3.3 Inclusion of Minorities

Only men are eligible for this trial. Different races and ethnicities and minorities will be sought for participation in this study.

3.4 Restrictions

Men enrolled in this study must practice acceptable methods of birth control to prevent pregnancy.

4.0 TREATMENT PLAN

4.1 Agent Administration

Treatment will be administered on an outpatient basis. Reported AEs and potential risks for calcitriol and ketoconazole are described below. No investigational or commercial agents or therapies other than those described below may be administered with the intent to treat the patient's malignancy. Calcitriol will be administered orally as 0.5 mcg caplets. Patients will be instructed to take calcitriol over a period \leq 15 minutes. Ketoconazole will be administered orally TID. The dose of ketoconazole will be at a standard dose, 400 mg TID. Hydrocortisone will be administered orally 20mg in the AM and 10mg PM starting the night prior to the first dose of calcitriol. The scheduling is detailed below.

Calcitriol will be given orally daily 10 mcg x 3 consecutive days per week starting on day 1 subsequently. On Day 1, ketoconazole will be started orally at 400 mg TID (Table 1). Hydrocortisone 20 mg every morning and 10 mg every evening will be given starting the evening before the first dose of calcitriol.

4.2 Treatment Schedule

Table 1

Calcitriol 10mcg QD X3, weekly + Ketoconazole 400mg po TID and Hydrocortisone 20mg AM, 10mg PM

Day	-1	1	2	3	4	5	6	7	8	9	10	11	12	13	14	15	16	17	18	19	20	21	22	23	24	25	26	27	28	
Calcitriol		C	C	C					C	C	C					C	C	C					C	C	C					
Ketoco Nazole		K	K	K	K	K	K	K	K	K	K	K	K	K	K	K	K	K	K	K	K	K	K	K	K	K	K	K	K	K
Hydro Cortisone	H	H	H	H	H	H	H	H	H	H	H	H	H	H	H	H	H	H	H	H	H	H	H	H	H	H	H	H	H	

K = ketoconazole 400 mg TID (1200mg/day).

C = Calcitriol.

H =Hydrocortisone 20mg AM, 10mg PM (starting in the evening before the first dose of calcitriol)

4.1 Supportive Care Guidelines

Patients should receive full supportive care, including antiemetics, antibiotics, transfusions of blood and blood products, etc., when appropriate. Whenever any medications are administered, the reason(s) for treatment, dosage and date of treatment must be recorded on the case report forms (CRFs).

Erythropoietin alpha can be administered concurrently.

4.2 Duration of Experimental Therapy

Experimental therapy consisting of calcitriol, hydrocortisone and ketoconazole will continue in the absence of disease progression and absence of unacceptable/ unmanageable drug-related AEs.

There will be no rest period between cycles. Cycle 2 will start on day 29 in the absence of dose delays.

Treatment will continue unless 1 of the following is satisfied:

- Disease progression (see section 6.3)
- Intercurrent illness that prevents further administration of treatment
- Unacceptable AE
- Patient decides to withdraw from the study
- General or specific changes in the patient's condition render the patient unacceptable for further treatment in the judgment of the investigator
- For up to one year if none of the above and if the treatment is still working at one year patients may discuss with the treating provider whether continuing calcitriol treatment is recommended but will not receive calcitriol as part of this study.

5.0 DOSING DELAYS/DOSE MODIFICATIONS

5.1 Ketoconazole

Dose interruptions should be the first approach to managing toxicity. Repeat dose interruptions are allowed as required. No dose reduction is allowed.

5.2 Dose Interruption for Non-Hematopoietic Toxicity

In the event of CTC Grade 3 or 4 non-hematopoietic AE(s) that the investigator considers due to suspected disease progression, re-evaluation of tumor status is indicated, irrespective of scheduled clinic visits.

CTC Grade 3 or 4 believed to be drug related will be considered DLTs and will result in taking patients off study. One exception will be in the case of CTC Grade 3 diarrhea or Grade 3 nausea that is not attributed to hypercalcemia. In those situations ketoconazole may be resumed after a period of interruption that does not exceed 2 weeks with full antiemetics or antidiarrheal medication. In the event that these toxicities recur at grade 3 or greater, despite adequate supportive medications, this will be a DLT and the patients will be taken off study.

Ketoconazole may also be interrupted for a period that does not exceed 2 weeks in the event of symptomatic intolerable Grade 2 rash. At a minimum, reassessment of toxicity should be done twice weekly and more frequently if clinically indicated. When the AE decreases in severity to CTC Grade 1, the patient may resume the assigned dose.

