5.7 Hypercalcemia

A possible side effect of calcitriol is hypercalcemia; therefore all calcium levels used for the determination of toxicity will be corrected for serum albumin levels using the following formula:

$$Ca^{+2}_{cor} = Ca^{+2}_{ser} + (0.8)(4.0 - Alb_{ser})$$

Patients developing:

- a) Corrected serum calcium ≥ 12 mg/dl persisting ≥ 7 days or
- b) Any corrected calcium ≥ 13 mg/dl with symptoms secondary to hypercalcemia
or
- c) Any corrected serum calcium ≥ 14 mg/dl

Calcitriol will be stopped and calcium level will be repeated in 1 week. Treatment will resume when calcium level returns to ≤ 10.5 mg/dl. Recovery from hypercalcemia must occur within 2

weeks to continuation on study. If this toxicity recurs, the patient will be taken off study. Further therapy off study would then be at the discretion of the treating physician.

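### Sections 5.2 and 5.7 conflict for a first drug-related Grade 3-4 event caused by hypercalcemia that recovers within 2 weeks: one removes the patient, the other lets treatment resume

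*Combined protocol and SAP*

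**What the plan says.** Section 5.2 (Dose Interruption for Non-Hematopoietic Toxicity) gives a general removal rule: "CTC Grade 3 or 4 believed to be drug related will be considered DLTs and will result in taking patients off study". It then allows a single departure: "One exception will be in the case of CTC Grade 3 diarrhea or Grade 3 nausea that is not attributed to hypercalcemia". In that situation ketoconazole may restart after an interruption of no more than 2 weeks, with supportive medication. A recurrence at Grade 3 or above is a DLT and takes the patient off study.

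Section 5.7 (Hypercalcemia) has three triggers, all on albumin-corrected calcium:
- (a) 12 mg/dl or more, persisting for at least 7 days
- (b) "Any corrected calcium ≥ 13 mg/dl with symptoms secondary to hypercalcemia"
- (c) "Any corrected serum calcium ≥ 14 mg/dl"

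The action is the same for all three: "Calcitriol will be stopped and calcium level will be repeated in 1 week". Treatment resumes when calcium is 10.5 mg/dl or below, and recovery must occur within 2 weeks for the patient to stay on study. Removal for a repeat episode is stated separately: "If this toxicity recurs, the patient will be taken off study".

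Section 6.4.1 names hypercalcemia among the common effects of high-dose calcitriol and lists nausea and vomiting among its early signs. Section 5.10 lists an unacceptable AE as a reason to discontinue, without defining the term.

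**The concern.** Section 5.2 does not merely overlook hypercalcemia. It names it, and does so in order to keep hypercalcemia-attributed nausea out of its only exception. An investigator reading 5.2 would conclude that Grade 3 nausea from hypercalcemia means removal at the first event. An investigator reading 5.7 would conclude that the same patient may go back on calcitriol once calcium recovers.

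The background describes hypercalcemia as the toxicity that limits calcitriol dosing, and the trial adds a CYP24 inhibitor in order to raise calcitriol exposure. An unclear rule here could lead to one patient being removed and another, with the same event, being re-exposed. It would also make the handling of this toxicity uneven across a trial that targets 15 evaluable patients.

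**Working it through.** No figure in the plan bears on this point, so the check sets the two rules side by side and applies them to one case.

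**Test case.** A first episode with these features:
- corrected calcium of at least 13 mg/dl, judged related to calcitriol
- Grade 3 nausea attributed to the hypercalcemia
- calcium back to 10.5 mg/dl or below within 2 weeks

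The calcium threshold, the recovery level and the 2-week limit come from 5.7. The nausea grade and attribution come from 5.2. The link between nausea and hypercalcemia comes from 6.4.1.

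| Step | Section 5.2 | Section 5.7(b) |
|---|---|---|
| Does the rule apply? | Yes: drug-related, Grade 3, non-hematopoietic | Yes: 13 mg/dl or more, with symptoms |
| Does an exception apply? | No: the exception requires nausea not attributed to hypercalcemia | None stated for Grade 3-4 events |
| First event | DLT, off study | Calcitriol held, calcium repeated in 1 week |
| Recovery within 2 weeks | No effect: already off study | Treatment resumes |
| Recurrence | Does not arise | Off study |

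The two columns cannot both be followed for this patient.

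**Where the sections agree.** Calcitriol stops at the first event under both. If calcium does not recover within 2 weeks, both end study participation. They part only when recovery comes in time.

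**How far the conflict reaches.**
- *Trigger (b) with symptoms below Grade 3.* Trigger (b) accepts symptoms of any grade, and 6.4.1 lists mild ones such as dry mouth and a metallic taste. The 5.2 rule needs a Grade 3 or 4 event, so low-grade symptoms do not set it off, and no conflict is shown.
- *Calcium values alone, including triggers (a) and (c).* Whether a given value is itself Grade 3 or 4 depends on cut-points that the documents do not print. They also cite more than one CTC version (9.1.2 refers to 4.3 and to 3; 12.2 refers to 4.03). A conflict cannot be shown from the documents for these.
- *Grade 3 or 4 symptoms attributed to hypercalcemia, with recovery in time.* The conflict is shown from the text, with no outside grading table.

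**Does anything else settle it?** Neither section refers to the other, and no order of precedence is stated. The unacceptable-AE entry in 5.10 does not say which rule defines it.

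**The case against.** The strongest reply is that the two sections can be read together. Sections 5.1 to 5.5 are written mainly around ketoconazole and 5.7 to 5.9 around calcitriol. The interruptions described in 5.2 are of ketoconazole. Section 5.7 is the later and more specific rule, with its own hold, resumption and removal criteria, and 5.8 likewise sets its own DLT rule for creatinine. On this view, the reference to hypercalcemia in 5.2 simply sends such cases to 5.7.

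That reading is plausible, but it is inferred. Section 5.2 is headed for non-hematopoietic toxicity in general, its trigger is drug-related toxicity, and its consequence is leaving the study, not only stopping ketoconazole. It allows one exception and contains no pointer to 5.7.

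A second reply uses 9.1.1.2, under which events secondary to another event are identified by their primary cause. Grade 3 nausea from hypercalcemia would then be recorded as hypercalcemia, whose grade the documents do not let us determine. But that section governs what is entered on the CRF, not treatment, and 5.2 itself speaks of nausea attributed to hypercalcemia.

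A third reply is that the situation may be rare. The calcitriol-dexamethasone study in 2.3.1 reports no dose reduction for hypercalcemia among 43 patients, and 2.3.3 reports no hypercalcemic patient in the calcitriol-paclitaxel study at doses up to 38 µg. None of these regimens included ketoconazole, so the rate in this trial remains unknown.

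What stands from these replies is the limit on scope: the sections diverge only for Grade 3-4 events with timely recovery.

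**Conclusion.** The concern holds in a narrow form. For a first drug-related Grade 3-4 event caused by hypercalcemia, with calcium recovering within 2 weeks, 5.2 removes the patient and 5.7 allows re-exposure, and the protocol does not say which governs. The conclusion rests on the ordinary meaning of the two sections and on the event being judged drug-related. It needs no numerical assumption. How many patients would be affected cannot be estimated from the documents.

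A reader might infer three stronger points that the documents do not support:
- **Every 5.7 trigger, or at least a calcium of 14 mg/dl or more, contradicts 5.2.** This needs calcium grade cut-points that are not printed.
- **The conflict costs the trial a measurable amount of power.** This would need an event rate for the combination and the share of PSA responders lost through removal. Neither is given, and a patient whose response was confirmed before removal would not be lost as a responder.
- **The DLT count is distorted in a way that changes a decision.** The calcitriol dose is fixed, and the design in Section 12.0 has no escalation or stopping boundary based on DLTs; 12.2 only tabulates toxicity.

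The case therefore rests on patient safety and consistent handling of an expected toxicity, not on the primary analysis. It should be fixed.

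**What to change.** The sponsor should reconcile 5.2 and 5.7. The text should state which section governs hypercalcemia and Grade 3-4 symptoms attributed to it, and whether a first such event that recovers within 2 weeks means removal or interruption. Each section should refer to the other; a reference in 5.10 would help but is not essential. The choice of clinical rule belongs to the sponsor, and this review takes no position on it.

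The cost is about one sentence in each section, submitted as a protocol amendment under 13.2. Sample size, decision rules and assessment schedule are unaffected.

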5.3 Nausea and/or Vomiting

In patients who have emesis and are unable to retain ketoconazole, every attempt should be made to obtain control of nausea and vomiting. The dose of ketoconazole may be repeated if emesis occurs within 30 minutes of taking the tablets.

5.4 Diarrhea

Diarrhea can be debilitating and on rare occasions is potentially life-threatening. Guidelines developed by an American Society of Clinical Oncology panel for treating chemotherapy-induced diarrhea are abstracted below.

Pharmacological approaches include the following:

- Diarrhea has been successfully managed with anti-diarrheal agents such as loperamide. Loperamide administered as an initial 4-mg dose followed by 2-mg doses every 4 hours. This dose and regimen is moderately effective.
- Clonidine, non-steroidal inflammatory drugs, and the serotonin antagonist cryoheptadine have been shown to be effective in controlling diarrhea associated with inflammation of the bowel.

The synthetic octapeptide octreotide has been shown to be effective in the control of diarrhea induced by fluoropyrimidine-based chemotherapy regimens when administered as an escalating dose by continuous infusion or subcutaneous injection. Octreotide can be administered at doses ranging from 100 micrograms twice daily to 500 micrograms 3 times daily, with a MTD of 2000 micrograms 3 times daily in a 5-day regimen.

In the event of:

- **CTC Grade 1 diarrhea.** No specific supportive care is usually needed or indicated.
- **CTC Grade 2 or 3 diarrhea.** If this occurs and immediate supportive care measures are begun (e.g. loperamide) ketoconazole should be discontinued for up to a maximum of 14 days, until resolution or the diarrhea has decreased in severity to CTC Grade 1.
- **CTC Grade 4 diarrhea will be declared a DLT**
- If a Grade 4 diarrhea is associated with hemodynamic collapse, the investigator should report it as an SAE and remove the patient from the trial.

5.5 Other Concomitant Therapy with Ketoconazole

If surgery is considered necessary for the patient, whenever possible at least 7 days should elapse after the last dose of ketoconazole before surgery is performed. Treatment may be restarted after adequate wound healing.

No concomitant use of the following drugs is allowed: phenytoin, carbamazepine, rifampicin, barbiturates, or St John's wort as these drugs induce CYP3A4 and may alter levels of ketoconazole and/or calcitriol.

In addition patients cannot receive the following agents while on study since ketoconazole is known to impair the metabolism of these drugs. Patients on these agents may enter trial if the agent of concern can be discontinued or an alternative drug can be utilized: alfentanil, alfuzosin, almotriptan, alprazolam, amiodarone, amitriptyline, amprenavir, aprepitant, aripiprazole, bepridil, bortezomib, bosentan, budesonide, buprenorphine, buspirone, carbamazepine, cilostazol, cisapride, cyclosporine, delaviridine, didanosine, digoxin, disopyramidedofetilide, donepezil, eletriptan, elperenone, fluticasone, fosamprenavir, galantamine, systemic griseofulvins, indinavir, levobupivacaine, lopinavir, midazolam, mifepristone, modafinil, nateglinide, nefazadone, nelfinavir, oxcarbazepine, pimozide, quetiapine, quinidine, repaglinide, rifabutin, rifampins, rifapentine, ritonavir, saquinavir, sildenafil, sirolimus, tacrolimus, tadalafil, tolterodine, theophyllines, tolterodine, trazolam, valdecoxib, vardenafil, ziprasidone, zanisamide

Ketoconazole requires acidity for dissolution and absorption. Patients taking antacid should wait 2 hours before taking ketoconazole. Patients may not take a proton pump inhibitor or H2 blockers while on ketoconazole.

Patients receiving oral hypoglycemic agents should be monitored carefully for hypoglycemia since the clearance of these agents may be reduced by ketoconazole.

International normalized ratio (INR) elevations, and/or bleeding events have been reported in some patients taking warfarin. Patients taking warfarin should be monitored regularly for changes in prothrombin time or INR.

5.6 Skin Adverse Events

A variety of agents can be used to manage skin rashes. These include mild-to-moderate strength steroid creams, topical or systemic antibiotics, topical or systemic antihistamines, and occasionally retinoid creams.

5.7 Hypercalcemia

A possible side effect of calcitriol is hypercalcemia; therefore all calcium levels used for the determination of toxicity will be corrected for serum albumin levels using the following formula:

$$Ca^{+2}_{cor} = Ca^{+2}_{ser} + (0.8)(4.0 - Alb_{ser})$$

Patients developing:

- a) Corrected serum calcium ≥ 12 mg/dl persisting ≥ 7 days or
- b) Any corrected calcium ≥ 13 mg/dl with symptoms secondary to hypercalcemia
or
- c) Any corrected serum calcium ≥ 14 mg/dl

Calcitriol will be stopped and calcium level will be repeated in 1 week. Treatment will resume when calcium level returns to ≤ 10.5 mg/dl. Recovery from hypercalcemia must occur within 2

weeks to continuation on study. If this toxicity recurs, the patient will be taken off study. Further therapy off study would then be at the discretion of the treating physician.

5.8 Renal Dysfunction

In the event where creatinine levels increase ≥ 2 mg/dL, calcitriol therapy will be withheld until creatinine decreases < 2.0 mg/dL. Sustained increases (> 72 hours) in creatinine of ≥ 2.5 mg/dL will constitute a DLT and will result in removal from study even in the absence of hypercalcemia

5.9 Other Concomitant Therapy with Calcitriol

Caution should be exercised when calcitriol is co-administered with calcium supplements as this might enhance hypercalcemia. All patients will be instructed to discontinue calcium supplementation. Thiazides decrease urinary excretion of calcium and will be a contraindication to this treatment.

Since hypercalcemia increases the risk of arrhythmias patients on digoxin will not be allowed on study.

5.10 Criteria for Discontinuation

Patients may be discontinued from trial treatment and assessments at any time at the discretion of the investigator(s). Specific reasons for discontinuing a patient from this trial are the following:

- Disease progression
- Intercurrent illness that prevents further administration of treatment
- Unacceptable AE
- Patient develops kidney stones
- Patient decides to withdraw from the study
- General or specific changes in the patient's condition render the patient unacceptable for further treatment in the judgment of the investigator

PSA progression is an increase of 50% above the nadir at a minimum of 5 ng/mL. (i.e. PSA must rise a minimum of 5 units)

If that criterion is reached patients will be declared to have PSA Progressive Disease (PD), **but:**

- a. If radiographs do not confirm PD
- b. PSA and symptoms are stable or improved from baseline
- c. Patient is in agreement

Investigator will have the discretion to continue investigational therapy until:

PSA achieves a level of $> 50\%$ of baseline

or

Radiographic or symptomatic PD

or

Patient wish to discontinue

The two options for categorizing withdrawal are either progressive disease (PD) or an AE (>1AE may be documented as a reason for withdrawal). Only 1 event will be captured as the cause of death. Note that death is an outcome and not an AE.

All trial treatment-related toxicities and SAEs must be followed up until resolution.

All patients who have new or worsening CTC Grade 3 or 4 laboratory values at the time of withdrawal must have further tests performed, and the results must be recorded appropriately. Until the laboratory values have returned to CTC Grade 1 or 2, unless these values are not likely to improve because of the underlying disease. In these cases, the investigators must record their opinions in the patients' medical records. Laboratory abnormalities should **not** be reported as AEs unless any criterion for a SAE is fulfilled, the laboratory abnormality causes the patient to discontinue from the study, or the investigator insists the abnormality should be reported as an AE.

At withdrawal all ongoing study-related toxicities and SAEs must be followed until resolution, unless in the investigator's opinion, the condition is unlikely to resolve due to the patient's underlying disease.

After withdrawal from treatment, patients must be followed up for existing AEs for 30 calendar days after administration of the last dose of trial drug. All AEs occurring during that period must be reported to the U.S. Food and Drug Administration and must be followed up until resolved, unless in the investigator's opinion the condition is unlikely to resolve because of the patient's underlying disease.

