8.0 MEASUREMENT OF EFFECT

8.1 RECIST

The modified Response Evaluation Criteria in Solid Tumors (RECIST) and Recommended NCI PSA Response Criteria will be used for this trial for objective tumor response assessment. The primary response objective of this trial is the PSA response rate. In patients with measurable disease CR and PR will be assessed by RECIST criteria. Measurable response is a secondary objective of the phase II portion of this study.

Overall responses for all possible combinations of tumor responses in target and nontarget lesions with or without the appearance of new lesions*

Target lesions	Nontarget lesions	New lesions	Overall response
CR	CR	No	CR
CR	Incomplete response/SD	No	PR
PR	Non-PD	No	PR
SD	Non-PD	No	SD
PD	Any	Yes or no	PD
Any	PD	Yes or no	PD
Any	Any	Yes	PD

CR = complete response; PR = partial response; SD = stable disease; and PD = progressive disease. See Appendix B for more details.

Responses should be confirmed at a follow-up visit at least 4 weeks later

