9.0 SAFETY EVALUATION

9.1 Adverse Events

9.1.1 Definitions

An adverse event or adverse experience (AE) is any untoward medical occurrence associated with the use of a drug in humans, whether or not considered drug related. Therefore, an AE can be ANY unfavorable and unintended sign (including an abnormal laboratory finding), symptom, or disease temporally associated with the use of a medicinal (investigational) product, whether or not considered related to the medicinal (investigational) product (attribution of ‘unrelated’, ‘unlikely’, ‘possible’, ‘probable’, or ‘definite’).

An AE is considered “unexpected” if it is not listed in the investigator brochure or is not listed at the specificity or severity that has been observed; or if an investigator brochure is not required or available, is not consistent with the risk information described in the general investigational plan in other study-related documents.

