12.2 Analysis of Secondary Endpoints

Toxicity will be graded according to the NCI CTC version 4.03 and relationship to study drug will be assessed. Toxicities will be tabulated by dose of calcitriol. All patients who receive study drug will be considered evaluable for toxicity.

Objective tumor response will be judged by monthly physical exam and radiographic evaluation which will be done q12 weeks. Patients will be considered evaluable for tumor response if they have at least two post-baseline tumor assessments at least 4 weeks apart, received study medication for 8 weeks or if they have evidence of disease progression.

Analysis of the correlative studies in section 8.0 will be descriptive.

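### Section 5.10 allows only progression or adverse event as the withdrawal category, although patient decision, one-year completion and some investigator decisions fit neither

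*Combined protocol and SAP*

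**What the plan says.** Section 5.10 (Criteria for Discontinuation) gives six reasons for stopping: progression, intercurrent illness, unacceptable adverse event, kidney stones, patient decision and investigator judgment. Three of them read:

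- "Patient decides to withdraw from the study"
- "Intercurrent illness that prevents further administration of treatment"
- "General or specific changes in the patient's condition render the patient unacceptable for further treatment in the judgment of the investigator"

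The section opens by giving the investigator discretion to discontinue a patient at any time. Later it sets a closed coding rule: "The two options for categorizing withdrawal are either progressive disease (PD) or an AE". More than one adverse event may be recorded as the reason, and death is treated as an outcome.

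Section 4.2 (Duration of Experimental Therapy) repeats most of the list, omits kidney stones, and adds a time limit: "For up to one year if none of the above". After that, calcitriol is no longer given as part of the study.

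Section 9.1.1 defines an adverse event as "any untoward medical occurrence associated with the use of a drug in humans, whether or not considered drug related", and section 9.1.2 provides attributions of unrelated and unlikely. The study calendar (7.0) requires radiologic documentation for patients taken off study for progression.

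On the analysis side, section 8.1 states: "The primary response objective of this trial is the PSA response rate". Toxicity and tolerability are a secondary objective (section 1). Section 12.2 tabulates graded toxicities but specifies no table of discontinuation reasons.

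**The concern.** The coding rule and the list of reasons stand in the same section and cannot both be followed. When a patient leaves by his own choice, the coordinator has to enter progression, enter an adverse event, or break the rule. This is an instruction that produces a false entry, which is worse than a missing detail.

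The loss falls on the record of why treatment stopped. A choice to leave that is entered as an adverse event inflates the apparent number of discontinuations for toxicity. The same choice entered as progression can hide poor tolerance that showed itself only as a wish to stop. In a single-arm trial of about 15 patients, readers will use that record to judge whether the combination can be taken for long. Appendix B, section 5 also asks that reasons for excluding patients from subanalyses be clearly reported, and gives early discontinuation as an example. A two-value code cannot supply those reasons.

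**Working it through.** **1. Do the plan's design figures depend on the code?** Inputs from section 12.0: stage 1 size n1 of 7 to 11, stopping at 0 responses; overall size n of 13 to 17; the largest response count that still rejects H1 is r = 2 for n = 13-14 and r = 3 for n = 15-17 (table bounds); true response rates 10% and 40%; equal weight on the 5 × 5 = 25 combinations.

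- Stopping at stage 1: (1 − p)^n1. At p = 0.10 this gives 0.478, 0.430, 0.387, 0.349 and 0.314 for n1 = 7 to 11. The mean is 0.392, against 39% stated.
- Declared active: the sum over x = 1 to n1 of P(X1 = x) × P(X2 ≥ r + 1 − x), with X1 binomial(n1, p) and X2 binomial(n − n1, p). Averaged over the 25 combinations this is 9.7% at p = 0.10 (stated: limited to 10%) and 93.5% at p = 0.40 (stated: 93%).

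All three figures reproduce. The inputs are response counts and patient numbers, so the withdrawal code does not enter and changing it alters none of them.

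**2. Does each listed exit have a truthful code under the two-option rule?**

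| Exit | Progression? | Adverse event (9.1.1)? | Result |
|---|---|---|---|
| Progression | yes | – | codable |
| Unacceptable adverse event | – | yes | codable |
| Kidney stones | – | yes | codable |
| Intercurrent illness | – | yes, when it meets the definition; may be attributed as unrelated | usually codable |
| Investigator judgment | only if present | only if present | no code when neither is present |
| Patient decision | no | no | no code |
| Completed one year (4.2) | no | no | no code |

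Patient decision is the clearest case. A choice is not a medical occurrence, and without progression there is nothing to supply the documentation that the study calendar requires.

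**3. Size.** One miscoded patient as a share of the permitted overall accrual:

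- 1/17 = 5.9%
- 1/15 = 6.7%
- 1/13 = 7.7%

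The documents give no withdrawal rate. If two or three of 15 patients left this way (an assumption), the shift would be 2/15 = 13.3 or 3/15 = 20.0 percentage points. Section 12.2 counts everyone who received study drug as evaluable for toxicity, so the true denominator could be somewhat larger than 13 to 17 and the shift correspondingly smaller.

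**The case against.** The strongest case on the other side is that little in the planned analysis uses the code. Section 12.2 defines no adverse-event discontinuation rate, so no specified result is shown to be wrong. Several exits also fit the rule truthfully. The adverse event definition requires no causal link, so intercurrent illness and kidney stones can be entered as adverse events, and the illness can be attributed as unrelated. Changes in a patient's condition that prompt an investigator's decision will often be progression or an adverse event. Reaching one year is arguably not a withdrawal at all.

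Most of this stands and limits the point, but it does not remove it. Patient decision still has no valid code, and the rule offers no third option.

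A reader might go further and infer that consent withdrawals and intercurrent illness would be counted as drug failures. The documents do not support that:

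- PSA response is judged from PSA values, with absence of clinical or radiological progression for a partial response (section 8.2). No rule turns a patient who met those criteria into a non-responder because of his withdrawal code.
- Appendix B, section 5 counts eligible patients with unknown response as failing to respond. A patient who leaves before assessment is therefore treated the same way there, whatever his code. For illustration, if 2 of 15 patients left early and counted as non-responders, the effective rate would be 0.40 × (1 − 2/15) = 0.347 and average power would fall from 93.5% to 86.6%. That loss comes from the missing assessment and not from the code.
- An adverse event code does not attribute the event to the drug.

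Nor does a false progression code by itself make a patient evaluable for tumor response. The condition in section 12.2 is "or if they have evidence of disease progression", which calls for evidence. The code could have that effect only if someone took it as evidence, and a short clarifying sentence would prevent this.

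**Conclusion.** The point holds as a minor error in a record-keeping rule. Followed as written, section 5.10 produces a false reason for patient decision, for completion of one year where that is recorded as a withdrawal, and for an investigator's decision made without progression or an adverse event. What is damaged is the description of why patients stopped, by 5.9 to 7.7 percentage points per miscoded patient over 17 to 13 patients. How many patients would be affected is unknown, since the plan states no expected withdrawal rate.

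The primary PSA response analysis, the go/no-go rule and the stated operating characteristics are unaffected. Linking the code to tolerability rests on the inference that discontinuation reasons will be read as evidence on that objective. The plan names tolerability as an objective but does not define a discontinuation rate as its measure.

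**What to change.** Replace the two-option sentence in section 5.10 with withdrawal categories that match the lists in sections 5.10 and 4.2 (Duration of Experimental Therapy):

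- progression
- adverse event
- patient decision
- investigator decision
- completed one year
- death, recorded as an outcome

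Keep kidney stones, and intercurrent illness that meets the adverse event definition, within the adverse event category or flag them as adverse events as well. Section 2.3.1 describes urinary tract stones as the only calcitriol-related toxicity in the earlier calcitriol and dexamethasone trial, so a separate single-choice category would understate toxicity. The two lists should also be reconciled with each other, because kidney stones appear only in section 5.10.

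Add to section 12.2 a table of discontinuations by reason, and a statement that the withdrawal code does not determine PSA response, tumor response or evaluability.

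The cost is one replaced sentence, one case report form field and one descriptive table. Sample size, decision bounds and the clinical rules for stopping treatment do not change.
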